The study protocol, documentation, data, and all other information generated will be held in strict confidence. No information concerning the study or the data will be released to any unauthorized third party without prior written approval from the lead PI.

The lead PI or delegate and the FDA may inspect all documents and records required to be maintained by the site PIs, including, but not limited to, medical records (office, clinic, or hospital) and pharmacy records for the participants in this study. The clinical study site will permit access to such records.

C.13.6 Study Discontinuation

The lead PI has the right to terminate this study or an individual site's participation at any time. Reasons for terminating the study may include, but are not limited to, the following:

- Incidence or severity of adverse events indicates a potential health hazard;
- Data recording is inaccurate or incomplete;
- Site PI does not adhere to the protocol or applicable regulatory guidelines in conducting the study.

C.13.7 Future Use of Stored Specimens

Any leftover stool specimens will be stored and may be used for future research, under a future protocol, to learn more about FMP-402. These specimens will be stored indefinitely after the study is completed. In the informed consent document, participants will be given an opportunity to choose whether or not their de-identified barcoded specimens are stored for future use. For participants who choose not to allow storage of their samples for future use, these samples will be destroyed at the end of the study.

There are no benefits to participants in the collection, storage and subsequent research use of specimens. Reports about future research done with participant's samples will NOT be kept in their health records, but participant's samples may be kept with the study records or in other secure areas.

Participants can decide if they want their samples to be used for future research or have their samples destroyed at the end of the study. A participant's decision can be changed at any time before the end of the study by notifying the study doctors or nurses in writing. However, if a participant consents to future use and some of their stool has already been used for research purposes, the information from that research may still be used.

Samples may be shared with other investigators at other institutions with the consent of the lead PI. Each sample will be encoded (labeled) only with a barcode and a unique tracking number to protect participant's confidentiality.

Research using stored specimens may be conducted by other institutions. Any specimens and data provided to the receiving-institution will be coded. Unequivocally, neither individual personal identifiers nor the key linking coded data to individuals will be released to the receiving-institution. The use of any of these specimens for any future studies will only be performed after the lead PI has authorized the use of these specimens.

C.14. DATA HANDLING AND RECORD KEEPING

The PIs are responsible to ensure the accuracy, completeness, legibility, and timeliness of the data reported. All data collection forms should be completed in a neat, legible manner to ensure accurate interpretation of data. Black ink is required to ensure clarity of reproduced copies. When making changes or corrections, cross out the original entry with a single line, and initial and date the change. Do not erase, overwrite, or use correction fluid or tape on the original.

Copies of the electronic CRF (eCRF) will be provided for use as source documents and maintained for recording data for each participant enrolled in the study. Data reported in the eCRF derived from source documents should be consistent with the source documents or the discrepancies should be explained.

C.14.1 Data Management Responsibilities

All source documents and laboratory reports must be reviewed by the clinical team and data entry staff, who will ensure that they are accurate and complete. Adverse Events must be graded, assessed for severity and causality, and reviewed by the site PI or designee as outlined above.

Data collection is the responsibility of the clinical trial staff at the site under the supervision of the site PI. During the study, the site PIs must maintain complete and accurate documentation for the study.

C.14.2 Data Capture Methods

Clinical data (including AEs, concomitant medications, and solicited events data) and clinical laboratory data will be entered into a 21CFR11-compliant Internet Data Entry System, RedCap. The data system includes password protection and internal quality checks, such as automatic range checks, to identify data that appear inconsistent, incomplete, or inaccurate. Clinical data will be entered directly from the source documents.

C.14.3 Types of Data

Data for this study will include clinical, safety and microbiological outcome measures.

C.14.4 Timing/Reports

Interim reports for the DSMB will be prepared when approximately 50% of treating participants complete enrollment and every 6 months. Interim statistical reports may be generated as deemed necessary and appropriate by the lead PI. Other safety summary reports may be generated for the DSMB. A final report will be prepared following the availability of all the clinical, safety and efficacy data.

C.14.5 Study Records Retention

Study files (except for future use consent forms) must be maintained for a minimum of two years after the last approval of a marketing application in an ICH region and until there are no pending or contemplated marketing applications in and ICH region or at least 2 years have elapsed since the formal discontinuation of clinical development of the investigational product. These documents should be retained for a longer period, however, if required by local regulations. No records will be destroyed without the written consent of the lead PI or designate, if applicable. It is the responsibility of the lead PI or designate to inform the site PIs when these documents no longer need to be retained. Consent forms for future use will be maintained as long as the sample exists.

C.14.6 Protocol Deviations

A protocol deviation is any noncompliance with the clinical trial protocol, GCP, or protocol-specific MOP requirements. The noncompliance may be either on the part of the participant, the site PI, or the study site staff. As a result of deviations, corrective actions are to be developed by the site and implemented promptly.

These practices are consistent with ICH E6:

- 4.5 Compliance with Protocol, Sections 4.5.1, 4.5.2, and 4.5.3
- 5.1 Quality Assurance and Quality Control, Section 5.1.1
- 5.20 Noncompliance, Sections 5.20.1, and 5.20.2.

It is the responsibility of the site PI/study staff to use continuous vigilance to identify and report deviations within five working days of identification of the protocol deviation, or within five working days of the scheduled protocol-required activity. All deviations must be promptly reported to the lead PI or designated personnel.

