C.2.3.1 Potential Risks

In the first randomized controlled trial on FMT, mild diarrhea (94%), abdominal cramping (31%) and belching (19%) were observed on the day of colonoscopic infusion; however, these symptoms resolved within 3 hours. Of note, in follow-up three patients who were treated with donor feces (19%) had constipation. No other adverse events related to the study treatment were reported.³⁶ Recently, Osman et al presented effectiveness and safety data from a 2,050 patient cohort among OpenBiome recipients. The data suggests that among the 42 suspected adverse events, 0 were definitely related to FMT material based on NIH criteria after a comprehensive investigation (Appendix 16.2).

There is a paucity of data on long-term follow-up related to FMT. Brandt et al conducted a retrospective multi-center study (n=77) with a follow up varying

between 3 to 68 months and reported 7 deaths. However, none related to FMT.³⁷ A recent systematic review on the safety of FMT, suggests there are risk including: infectious (fever, bacteremia), autoimmune disease (peripheral neuropathy, Sjogren's syndrome, idiopathic thrombocytopenic purpura and rheumatoid arthritis, inflammatory bowel disease flare among patients with ulcerative colitis) and other studies have suggested a link to metabolic syndrome.^{38, 39} However, comprehensive screening of donors should decrease any potential future risk. Donors are highly selected with only 2.8% of candidate donors qualifying to donate after screening both infectious disease and microbiome-mediated disease (Appendix 16.3).

C.2.3.2 Potential Benefits

Studies have suggested that FMT may be able to decolonize patients colonized with VRE, and in turn, the prevention of VRE associated infection. As described previously, our group has demonstrated in a retrospective study that allogenic FMT is able to decolonize VRE significantly more than autologous FMT (Appendix 16.1). Additionally, a number of case reports have reported decolonization of ARB following FMT, including carbapenem-resistant Enterobacteriae (CRE), extended spectrum beta-lactamase (ESBL)-producing *Escherichia coli* and methicillin-resistant *Staphylococcus aureus* (MRSA) enteritis.²³⁻²⁹

C.3. OBJECTIVES

C.3.1 Study Objectives

To investigate the efficacy and safety of FMP-402 to decolonize VRE.

Primary Objectives:

- To determine the VRE decolonization rate of FMP-402 versus placebo.
- To evaluate the safety profile for FMP-402 versus placebo.

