5. Males must agree to avoid impregnation of women during and for four weeks after completing study treatment. through use of an acceptable method of contraception.

Note: §Includes, but is not limited to, barrier with additional spermicidal foam or jelly, intrauterine device, hormonal contraception (started at least 30 days prior to study enrollment), intercourse with men who underwent vasectomy.

C.5.2 Participant Exclusion Criteria

Participants will not be able to participate if they meet any of the following exclusion criteria:

1. Female patient who are pregnant, lactating or planning on becoming pregnant during study. Female patients of childbearing potential will undergo a pregnancy test, and be excluded from the study if positive.
2. Inability (e.g. dysphagia) to or unwilling to swallow capsules.

3. Active antibiotic-resistant bacteria (ARB) or gastrointestinal infection at time of enrollment.
4. Patient received antibiotics in the last 48 hours. Patients will be eligible to enroll if antibiotic therapy is discontinued for at minimum 48 hours prior to randomization. Does not include antibiotics used for prophylaxis or topical antibiotics.
5. Requires continued antibiotic use or anticipates antibiotic use in the upcoming 4 weeks. Does not include antibiotics used for prophylaxis or topical antibiotics.
6. Unwilling to withhold probiotics for a minimum of 48 hours prior to providing a screening stool sample.
7. Known or suspected toxic megacolon and/or known small bowel ileus.
8. Major gastrointestinal surgery (e.g. significant bowel resection) within 3 months before enrollment. This does not include appendectomy or cholecystectomy.
9. History of total colectomy or bariatric surgery.
10. Admitted to or expected to an intensive care unit for medical reasons (not just boarding). Patients residing in a nursing home, long-term care facility or rehabilitation center may be enrolled.
11. Concurrent intensive induction chemotherapy, radiation therapy or biological treatment for active malignancy. Patients on maintenance chemotherapy may be enrolled only after consultation with medical monitor.
12. Unable or unwilling to comply with protocol requirements.
13. Expected life expectancy < 6 months
14. Previous FMT or microbiome-based products at any time excluding this study.
15. Patients with a history of severe anaphylactic or anaphylactoid food allergy.
16. Solid organ transplant recipients ≤ 90 days post-transplant or on active treatment for rejection.

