Placebo capsules will be identical in appearance to FMP-402 capsules but will not have human feces, [REDACTED]

[REDACTED] processed as described in OpenBiome's BBMF #

17300 [REDACTED]

C.6.3. Product Storage and Stability

Produced material will be stored at -80°C and each unit will have a date of production printed on it for tracking purposes. Studies have been conducted to ensure long-term bacterial viability following the freezing process based on studies conducted by Hamilton et. al and Youngster et. al.^{40,41} Local site storage at -20°C will be permitted for up to 6 months.

FMP-402 is currently undergoing stability testing, therefore expiration dates will not be provided with each unit. Instead, storage requirements will be provided via correspondence from the manufacturing company, Finch Therapeutics. Results from ongoing stability testing will be provided by Finch Therapeutics to partner sites, through OpenBiome, on an anticipated monthly basis. If units are determined to be unstable, Finch Therapeutics will communicate with OpenBiome to destroy the relevant units.

C.6.4 Dosage, Preparation and Administration of Study Intervention/Investigational Product

Participants will receive a single dose of 30 FMP-402 or placebo capsules. The dosing rationale is driven by the successful VRE decolonization for 2 patients with recurrent CDI and co-colonization of VRE following a single dose of 30 OpenBiome FMT capsules. Participants will undergo capsule administration by the following process:

- Document Review: Confirmation/review of exclusion criteria/contraindications as previously described.
- Safety Capsules: Direct observed capsule test, where participants will ingest one inert, size 00 ‘safety’ capsule under direct supervision of the study physician/nurse.
- Dietary instructions: Patients should maintain a clear liquid diet the day of administration and should fast (NPO) for a minimum of 2 hours prior to administration
- Capsule administration:
 - a. Patient should ingest 30 capsules (FMP-402 or placebo) under the direct observation of a physician/nurse. Patients may have water during capsule administration.
 - b. Patient should ingest capsules after extraction from freezer, and no longer than 60 minutes after removal.
 - c. Patients should remain fasting (NPO) for 1 hour following ingestion but may then return to a full diet.

C.6.5 Accountability Procedures for the Study Intervention/Investigational Product

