The site principal investigator (PI) (or designee) will maintain an accurate record of the receipt of the investigational materials as shipped, including the date received. One copy of this receipt will be returned to OpenBiome when the contents of the investigational materials shipment have been verified. In addition, the unblinded laboratory technician based at OpenBiome will maintain a log of all clinical trial materials (FMP-402 and placebo) dispensed. This clinical trial material accountability record will be available for inspection at any time.

C.6.6 Modification of Study Intervention/Investigational Product for a Participant

If the participant is unable to complete the full dose of FMP-402 or placebo, the following modification will take place. The dose will be recorded and the remainder of capsules will be offered to participant the same day at the discretion of the treating physician. Intention-to-treat analysis will be utilized according to best practices in clinical trials.

C.6.7 Assessment of Participant Compliance with Study Intervention/Investigational Product

FMP-402 or placebo capsules will be consumed under direct supervision of study staff.

C.6.8 Concomitant Medications/Treatments

Given the participants with VRE colonization and who are most at risk for VRE infection are patients with multiple comorbidities, all medications will be accepted in this study, at the discretion of the treating physician. This includes, but is not limited to:

1. Anti-hypertensive therapies
2. Heart failure medications
3. Diuretics
4. Laxatives
5. Topical medications
6. Anti-depressants
7. Statins
8. Diabetic medication

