- f) At the time of VRE infection (for subjects who experience an infection) or serious AE. Stool samples will attempt to be collected (optional). Additionally, VRE isolates from the site of associated VRE infection (blood, urine, wound) will attempt to be collected (optional) for participants suspected to have a VRE infection.

C.8. ASSESSMENT OF SAFETY

Safety will be assessed by the frequency and severity of adverse events (AE)

C.8.1 Definition of an Adverse Event (AE)

Adverse events (AEs) will be recorded at each regular scheduled study visit in the study patient record (source document) as well as on a specific AE case report form (CRF).

An AE is any untoward medical occurrence in a study patient or clinical investigation participant administered a pharmaceutical product. An AE does not necessarily have a causal relationship with this treatment. An AE can therefore be any unfavorable and unintended sign (including an abnormal laboratory finding), symptom, or disease temporally associated with the use of a medicinal product, whether or not related to the medicinal product, e.g.:

- any new clinical diagnosis

- any symptom that requires medical clarification or leads to in-patient admission (surgery or accident)
- any suspected adverse drug reaction (ADR)
- any symptom that appears on the study patient's medical records
- any event related in time with the application of the study medication and affecting the health of the study patient (including laboratory value changes)

If there is any doubt as to whether a clinical observation is an AE, the event should be reported. AEs must be graded for severity and relationship to study product. Adverse events of special interest (AESI) will be defined as newly acquired transmissible infectious diseases (e.g. newly acquired bacteremia).

C.8.2 NIH Grading of Severity of the Event

AEs will be assessed by the clinician using the NIH Common Terminology Criteria for Adverse Events (CTCAE) defined grading system (Appendix 17.3). Briefly, the criteria for estimating adverse event severity grade:

- **Grade 1, Mild:** Asymptomatic or mild symptoms; clinical or diagnostic observations only; intervention not indicated.
- **Grade 2, Moderate:** Minimal, local or noninvasive intervention indicated; limiting age-appropriate instrumental activities of daily living (ADL).

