- **Grade 3, Severe:** Severe or medically significant but not immediately life-threatening; hospitalization or prolongation of hospitalization indicated; disabling; limiting self-care ADL.
- **Grade 4, Life threatening:** Places the patient or subject at immediate risk of death. It does not include an adverse event that, had it occurred in a more severe form, might have caused death.
- **Grade 5, Death**

C.8.3 Relatedness

All adverse events, regardless of relatedness should be reported. All adverse events should be evaluated for relatedness when reporting and documenting on the CRF.

The following guidelines of relatedness are used modified from the NIH guidelines:

Related: The adverse event is related to the FMT material – i.e. an event that follows a reasonable temporal sequence from administration of the FMT material, follows a known or expected response pattern to the FMT material, that is

confirmed by improvement on stopping and reappearance of the event on repeated exposure and that could not be reasonably explained by the known characteristics of the patient's clinical state.

Not Related: The adverse event is not related to the FMT material. - i.e. another cause of the event is most plausible; and/or a clinically plausible temporal sequence is inconsistent with the onset of the event and the study intervention and/or a causal relationship is considered biologically implausible.

C.8.4 Solicited Adverse Events after FMT

In addition to open-ended questions on adverse events meeting the above definitions, specific potential adverse events will be inquired about during the follow up period (following intervention through to 6 months after randomization):

Symptom that is clinically more severe than participant's baseline	Severity				
	Grade 1	Grade 2	Grade 3	Grade 4	Grade 5
Fever*	38.0 - 39.0 degrees C (100.4 - 102.2 degrees F)	>39.0 - 40.0 degrees C (102.3 - 104.0 degrees F)	>40.0 degrees C (>104.0 degrees F) for <=24 hrs	>40.0 degrees C (>104.0 degrees F) for >24 hrs	Death
Diarrhea	Increase of <4 stools per day over baseline pre-FMT; mild increase in ostomy output compared to baseline	Increase of 4 - 6 stools per day over baseline; moderate increase in ostomy output compared to baseline; limiting instrumental ADL	Increase of >=7 stools per day over baseline; incontinence; hospitalization indicated; severe increase in ostomy output compared to baseline; limiting self-care ADL	Life-threatening consequences; urgent intervention indicated	Death

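### C.8.3 makes reappearance on repeated exposure a condition for a related AE, which a single-dose trial can almost never show, so two halting rules may fail to count plausibly caused events

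*Combined protocol and SAP*

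**What the plan says.** C.8.3 introduces its two categories with "The following guidelines of relatedness are used modified from the NIH guidelines".

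- **Related** needs reasonable timing, a known or expected response pattern, an event that is "confirmed by improvement on stopping and reappearance of the event on repeated exposure", and no reasonable explanation in the patient's clinical state. The conditions are joined by 'and'.
- **Not Related** has its own tests: "another cause of the event is most plausible; and/or a clinically plausible temporal sequence is inconsistent with the onset of the event", or a causal link that is biologically implausible.

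On exposure, C.6.4 states "Participants will receive a single dose of 30 FMP-402 or placebo capsules". If the dose is not finished, C.6.6 says "the remainder of capsules will be offered to participant the same day", at the treating physician's discretion. Exclusion 14 in C.5.2 is "Previous FMT or microbiome-based products at any time excluding this study".

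C.8.1 makes the assessment compulsory: "AEs must be graded for severity and relationship to study product". C.8.7 lists three levels for non-serious reactions, including a possibly-related level that C.8.3 does not define.

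C.8.9.1 suspends enrollment and dosing pending DSMB review in three situations, numbered here in the order listed. Rule 1 is three or more participants in a group with a Grade 3 AE in the same organ system deemed related. Rule 2 is any related SAE, with donor-to-recipient pathogen transmission named as included. Rule 3 is a pattern of events that the Medical Monitor considers related.

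**The concern.** Requiring reappearance on re-exposure suits a repeat-dose drug, where treatment can be stopped and restarted. Here there is no planned second exposure, so the condition excludes nearly every event regardless of its cause. Because the not-related category needs positive evidence of its own, such an event does not fall into it by default and is left without a category.

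That matters because relatedness decides whether rules 1 and 2 operate. If assessors follow the text, plausibly caused Grade 3 events and SAEs do not trigger the pause. If they use judgement instead, they have no written standard, and two assessors could score the same event differently. Either way, the suspension rules are less dependable than they look.

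**Working it through.** **Can each condition for Related be met after one dose?**

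| Condition | After a single 30-capsule dose |
|---|---|
| Reasonable timing | Can be met |
| Known or expected pattern | Can be met for expected events |
| Improvement on stopping | Improvement can be seen: C.2.3.1 reports from an earlier FMT trial that "these symptoms resolved within 3 hours". The words 'on stopping' fit a single dose poorly |
| Reappearance on repeated exposure | Cannot be met, except possibly where an unfinished dose is completed the same day (C.6.6) |
| Not explained by clinical state | Can be met |

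The obstacle is reappearance. A fatal event shows it most plainly: death is an SAE outcome in C.8.5 and cannot recur.

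**Does such an event fit Not Related?** Take an event with plausible timing, a plausible mechanism and no better cause. It fails all three not-related tests, so it fits neither category and adds nothing to rule 1 or to the general part of rule 2. The pathogen-transmission clause of rule 2 remains usable.

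**How many enroll before a scheduled look?** Planned enrollment is 46 over 11 months (Protocol Summary). C.14.4 gives DSMB reports at about 50% enrollment and every 6 months. At even accrual (assumed):

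- 50% point: 46 × 5.5/11 = 23 participants
- 6 months: 46 × 6/11 = 25.1 participants

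With 1:1 allocation, about 12 or 13 of these would have received FMP-402. This is the most exposure, and only if no ad hoc review, SUSAR referral, rule 3 or discretionary halt comes sooner.

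**Illustration for rule 1.** Let p be the assumed rate of product-caused Grade 3 events in one organ system and f the share of them scored Related. With 23 in the group and q = p × f,

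P(3 or more) = 1 − Σ (k = 0 to 2) C(23, k) q^k (1 − q)^(23 − k).

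For p = 10% and f = 1: 1 − (0.0886 + 0.2265 + 0.2768) = 0.408.

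| p (assumed) | all scored Related | half | 10% (split doses only, assumed) | none |
|---|---|---|---|---|
| 5% | 0.11 | 0.02 | 0.0002 | 0 |
| 10% | 0.41 | 0.11 | 0.0015 | 0 |
| 20% | 0.87 | 0.41 | 0.011 | 0 |
| 30% | 0.98 | 0.69 | 0.031 | 0 |

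**Illustration for the general part of rule 2.** One event suffices, so P = 1 − (1 − q)^23.

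| caused SAE rate (assumed) | all scored Related | 10% | none |
|---|---|---|---|
| 2% | 0.37 | 0.045 | 0 |
| 5% | 0.69 | 0.109 | 0 |
| 10% | 0.91 | 0.206 | 0 |

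**A rate from the documents.** The 2,050-patient cohort in C.16.2, mostly lower-GI delivery, had 3 possibly related AEs: 3/2,050 = 0.15%. At that rate rule 1 has a chance of about 0.000005 even if every event is scored Related.

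The documents give none of the rates in the two tables, so these show direction, not expected size.

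**The case against.** The best counter-argument is that the halting rules were not meant to depend on the literal text of C.8.3. That section calls itself guidelines and no halting rule cites it. Rule 1 says 'deemed' and rule 3 says 'considers'. Rule 2 gives pathogen transmission as an example of a related event, although a single dose would not show transmission by reappearance. C.8.7 provides for unexpected serious reactions, which a literal reading of C.8.3 would also bar because it asks for an expected pattern. A middle level may be set out in the C.17.4 flow chart, which is not shown here. The C.17.3 table is broken in this text, so nothing is argued from either appendix.

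There are also other routes to action: site PI review of every SAE within 24 hours, SUSAR referral to the DSMB, DSMB review of all SAEs every 6 months or ad hoc, a required comment on possible causation in each SAE report, DSMB review of non-serious reactions including possibly related ones, rule 3, and the PIs' power to halt (C.5.3.5). The event rates in the illustration are assumed, and the one rate from the documents makes rule 1 very unlikely to trigger under any wording.

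Most of this stands, and it limits the consequence: a plausibly caused SAE would still reach the DSMB, and sensible assessors may ignore the reappearance test. It does not remove the defect. These are the only relatedness definitions in C.8.3. Falling back on judgement leaves assessors without a standard, and C.8.7 attaches no suspension to SUSAR or SAE review, while rule 3 and PI halts are discretionary.

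**Conclusion.** The concern holds. As written, the related category is practically unattainable in this single-dose design, a plausibly caused event has no category, and C.8.3 and C.8.7 use different scales. Applied literally, rule 1 and the general part of rule 2 would not count such events; applied with judgement, scoring may differ between assessors.

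The practical loss is the automatic suspension before DSMB review, not the review itself. Its upper bound is the 23 to 25 enrolled participants worked out above, which assumes even accrual and no earlier action by another route. How often this would matter cannot be estimated from the documents. The primary safety endpoints count AEs, SAEs and AESIs without regard to relatedness and are unaffected. This should be fixed, but it does not undermine the trial's main comparisons.

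**What to change.** - In C.8.3, remove reappearance on repeated exposure as a requirement and reword the improvement condition for a single dose.
- Define Related, or a possibly-related level, as a reasonable possibility that the product caused the event.
- Use the same scale in C.8.3 and C.8.7, and check that the C.17.3 form matches.
- State in C.8.9.1 which levels count toward rules 1 and 2. The numerical thresholds need no change.

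The cost is a wording amendment to three sections and a check of one field on the AE form. A few more events may be scored as possibly related and lead to a suspension and DSMB review.
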